8.1.7 Overall Survival (OS)

Time to death for a given subject will be defined as the number of days from the date of first dose of study drug to the date of the subject's death. All events of death will be included, regardless of whether the event occurred while the subject was still taking study drug, or after the subject discontinued study drug. If a subject has not died on or before the "Cutoff" date, and there is any data (survival follow-up, study visit, death date, etc.) confirming that the subject is still alive or dies after the "Cutoff" date, the data will be censored at the "Cutoff" date; otherwise the data will be censored at the date when the subject was last known to be alive.

For each analysis datasets, the distribution of OS will be estimated using Kaplan-Meier methodology. Median survival time with the corresponding 95% CI will be provided from Kaplan-Meier estimation.

OS will be summarized for all subjects, subjects achieving CR, subjects achieving CRh, and non-CR/non-CRh subjects.

8.1.8 Post Baseline Transfusion Independence Rate (RBC/Platelet) and Duration of Post Baseline Transfusion Independence

The transfusion data was designed to be collected during the treatment period and until the 30 day follow-up visit. Therefore, the evaluation period for the post baseline transfusion independence is from the first dose of study drug to the last dose of study drug + 30 days, disease progression (including clinical progression), or death, whichever is earlier. Thus, post baseline transfusion independence is defined as a period of at least 56 days (≥ 56 days) with no RBC or platelet transfusion during the evaluation period.

Post baseline transfusion independence rate will be estimated as the proportion of subjects known to achieve transfusion independence during the evaluation period. The corresponding 95% CI for transfusion independence rate will be provided based on the binomial distribution (Clopper-Pearson exact method).

In addition, the baseline transfusion independence rate, which is defined as the proportion of subjects who received no transfusion within 56 days prior to the first dose of study drug (Studies M14-358 and M14-387) or 28 days (Study M14-212) prior to the first dose of study drug, will also be summarized. An analysis based on the definition of baseline transfusion independence as 28 days on or prior to the first dose of study drug will also be performed for all studies.

Number and percentage of subjects who were transfusion dependent at baseline and then become transfusion independent during the evaluation period will be provided. Number and percentage of subjects who were transfusion-independent at baseline and remain transfusion-independent during the evaluation period will also be provided.

In addition to the transfusion independence rate, the duration of transfusion independence will also be summarized. The duration of transfusion independence is defined as the 1st time period that a subject receives no RBC/platelet transfusions for at least 56 days during the evaluation period. The descriptive statistics (median and range) will be provided for duration of transfusion independence.

All transfusion data available in the extracted database will be used in the analyses of transfusion independence rate and duration of transfusion independence. The above analyses will also be performed separately for

- RBC transfusion
- Platelet transfusion.

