All local reader evaluations of the ECGs will be entered into the electronic case report form (eCRF). If the global interpretation is Abnormal (NCS or CS), the local reader will provide further information (e.g., sinus bradycardia, arrhythmia). The QT interval measurement will be documented in the eCRF only if a "prolonged QT" is observed. Correction by the Fridericia formula (QTcF) is preferred; however, correction by other methods may be acceptable based on discussion with the AbbVie medical monitor. The original ECG tracing will be retained as source documentation in the subject's records at the study site.

Multiple Gated Acquisition Scan (MUGA)/2D Echocardiogram with Doppler

Assessment of ejection fraction will be made at Screening by either a MUGA (preferred method) or 2D echocardiogram with Doppler provided that such assessment would not inappropriately delay therapy per discretion of the investigator. Subsequent evaluation will be made as clinically indicated for subjects who develop signs of cardiac compromise. It is preferred that the same method of assessment is used for a given subject.

Bone Marrow Aspirate and Biopsy

A bone marrow aspirate and biopsy will be done at Screening, at Cycle 2 Day 1, Cycle 4 Day 1, and every 3 cycles thereafter for response assessment until two successive bone marrow biopsies demonstrate CR then will be repeated if clinical evidence for recurrence occurs. Historical bone marrow aspirates at screening will not be sufficient, a bone marrow aspirate and biopsy must be performed for study entry to collect mandatory biomarker assessments. Flow cytometry may be used to detect the presence of abnormal cell phenotypes (based on the inappropriate expression of myeloid lineage markers). Minimal residual disease status may be determined, based on the phenotypic markers

detected in the screening sample. Bone marrow aspirates and/or biopsies performed as standard of care throughout the study should also be captured on an eCRF.

Note: For all study visits after Screening, bone marrow aspirates and/or biopsies may be performed within 7 days of the anticipated Day 1 visit of the subsequent cycle. Bone marrow aspirates and/or biopsies should be performed and resulted prior to drug dispensation beginning with Cycle 4 Day 1 visit.

A sufficient bone marrow aspirate (biopsy) must be collected for clinical assessment and predictive biomarker assessments.

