- CRh: all of the following criteria are met: Bone marrow with $< 5\%$ blasts, peripheral neutrophils of $\geq 0.5 \times 10^3/\mu\text{L}$, and peripheral platelets $\geq 0.5 \times 10^5/\mu\text{L}$ **

* Transfusion independence is defined as the absence of any RBC or platelet transfusion during any consecutive 8 weeks during the treatment period.³⁹

** For a bone marrow sample collected before the last cycle of study treatment, the hematology lab results collected from the date of bone marrow sample collection up to Day 1 of a subsequent cycle of study treatment will be used for CRh analysis. For a bone marrow sample collected during or after the last cycle of study treatment, the hematology lab results collected within 14 days after bone marrow sample collection date will be used for CRh analysis.

Reporting of Results

All dosed subjects will be assessed for response to treatment based on the published guidelines. Assessments will be performed at Cycle 2 Day 1, Cycle 4 Day 1, and every 3 cycles thereafter for response assessment until two successive bone marrow samples document a CR. When additional bone marrow evaluations are routinely indicated for clinical management, additional collection of bone marrow aspirate and peripheral blood are strongly encouraged as these findings have the potential to define either remission status or potential progression of leukemia. NOTE: For subjects who achieve CR or CRi, MRD status may be determined.

Subjects will be assigned to one disease state for best IWG response assessment, achievement of protocol defined hematologic response, and minimal residual disease positivity at the time of the best response.

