8.1.1 Complete Remission (CR) Rate

Complete Remission (CR) is a response based on investigator report using modified IWG criteria for AML.

Complete Remission (CR) rate will be defined as the proportion of subjects who achieve a complete remission at any time point during the study per the modified IWG criteria for AML. Subjects who never achieve CR or have no IWG disease assessment will be considered to be non-responders in the calculation of CR rate. In addition to the CR rate, the 95% confidence interval for CR rate based on the binomial distribution (Clopper-Pearson exact method) will be provided. The disease assessment collected after the post-treatment therapy will be excluded.

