8.1.2 CRh Rate

CRh (Complete remission with partial hematologic recovery) is a derived response based on bone marrow blast and hematology lab values. A Subject achieves a CRh when meeting the following criteria:

- Bone marrow with < 5% blasts and
- Peripheral blood neutrophil count of $> 0.5 \times 10^3/\mu\text{L}$ and
- Peripheral blood platelet count of $> 0.5 \times 10^5/\mu\text{L}$ and
- A 1 week (≥ 7 days) platelet transfusion-free period prior to the hematology lab collection.

For a bone marrow sample collected before the last cycle of study treatment, the hematology lab results collected from the date of the bone marrow sample collection up to the Day 1 of a subsequent cycle of study treatment will be used for CRh analysis.

For a bone marrow sample collected during or after the last cycle of study treatment, the hematology lab results collected within 14 days after bone marrow sample collection date will be used for CRh analysis.

CRh rate will be defined as the proportion of subjects who achieve CRh as the best response at any time point during the study. Subjects who never achieve CRh or have not had disease assessment or hematology data will be considered to be non-responders in the calculation of CRh rate. In addition to the CRh rate, the 95% confidence interval for CRh rate based on the binomial distribution (Clopper-Pearson exact method) will be provided. The disease assessment collected after the post-treatment therapy will be excluded for above analyses.

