8.1.3 CR + CRh Rate

CR + CRh rate will be defined as the proportion of subjects who achieve CR or CRh at any time point during the study. Subjects who never achieve CR/CRh or have no disease assessment will be considered to be non-responders in the calculation of CR + CRh rate. In addition to the CR + CRh rate, the 95% confidence interval for CR + CRh rate based on the binomial distribution (Clopper-Pearson exact method) will be provided.

The time to the 1st response of CR + CRh is defined as number of days from the 1st date of study drug to the 1st response of CR + CRh. The time to the best response of CR + CRh is defined as number of days from the 1st date of study drug to the 1st date of best response of CR + CRh.

The medians and ranges of time to the 1st response of CR + CRh and time to the best response of CR + CRh for all subjects, as well as for subjects with best response CR or best response of CRh will be summarized.

The disease assessment collected after the post-treatment therapy will be excluded for above analyses.

8.1.4 CR + CRh Rate by Initiation of Cycle 2

CR + CRh rate by initiation of Cycle 2 will be defined as the proportion of subjects who achieve CR or CRh by initiation of Cycle 2 of study treatment. Subjects who never achieve CR or CRh or have not had disease assessment by initiation of Cycle 2 will be

considered to be non-responders in the calculation of CR + CRh rate by initiation of Cycle 2. In addition to the CR + CRh rate by initiation of Cycle 2, the 95% confidence interval for CR + CRh rate by initiation of Cycle 2 based on the binomial distribution (Clopper-Pearson exact method) will be provided.

The disease assessment collected after the post-treatment therapy will be excluded for above analysis.

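### OS runs from first dose but is split by CR/CRh reached at any later time, so responders look better in expectation even if response has no bearing on survival; no landmark OS is planned

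*SAP*

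**What the plan says.** SAP 8.1.7 defines time to death as "the number of days from the date of first dose of study drug to the date of the subject's death". Survival is estimated by Kaplan-Meier, with medians and 95% confidence intervals, and is then split: "OS will be summarized for all subjects, subjects achieving CR, subjects achieving CRh, and non-CR/non-CRh subjects".

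The groups come from SAP 8.1.1 to 8.1.3. The CR rate is "the proportion of subjects who achieve a complete remission at any time point during the study", and the CRh rate is "the proportion of subjects who achieve CRh as the best response at any time point during the study". Subjects with no disease assessment count as non-responders. Assessments made after post-treatment therapy are left out.

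Protocol 5.3.3 sets the timing of response: "Assessments will be performed at Cycle 2 Day 1, Cycle 4 Day 1, and every 3 cycles thereafter for response assessment". Under Protocol 5.3.1.1 the marrow "may be performed within 7 days of the anticipated Day 1 visit of the subsequent cycle", and unscheduled marrows are possible.

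Three other parts of the SAP come near the point:

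- Section 8.1.4 gives "the proportion of subjects who achieve CR or CRh by initiation of Cycle 2 of study treatment", but only as a rate.
- Section 8.1.3 summarizes "The medians and ranges of time to the 1st response of CR + CRh".
- Section 8.1.11 lists OS sensitivity analyses that change the censoring or the deaths counted, but neither the grouping nor the time origin.

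Section 8.1.12 splits OS among responders by best post-baseline MRD value.

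**The concern.** The grouping variable is known only after the clock has started, and a subject must be alive to acquire it. Time from first dose to response is therefore guaranteed survival for responders, and deaths before an assessment go to the non-CR/non-CRh group. This is immortal-time bias. It favours responders in expectation, whether or not response prolongs survival.

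Nothing in the plan removes it. Section 8.1.4 does fix a responder set at an early point, but that set is not carried into OS, and its denominator still includes subjects who die before Cycle 2. Section 8.1.9 counts several other endpoints from 60 days after first dose, but not OS, and it still groups by ever-response.

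The study has no control group (Protocol 5.6.1), so median OS for CR, CRh and non-responders invites the reading that response carries a survival benefit of the size shown. OS by best MRD can be affected in the same way, because subjects who live longer can give more samples.

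**Working it through.** **The plan's own figure.** SAP Table 7 gives a targeted CR rate of 21% (13%, 31%) with N = 82. An exact Clopper-Pearson interval for 17/82 = 20.7% is 12.6% to 31.1%, which agrees.

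**Inputs from the documents.** 28-day cycles; assessments at Cycle 2, 4 and 7 Day 1 (Days 29, 85 and 169); a response share near 21%.

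**Assumed, because the documents do not give them.** Median OS of 6, 10 or 12 months; follow-up to 24 months (730.5 days); Weibull survival with shape 0.8 (falling hazard), 1.0 (constant) or 1.3 (rising, plausible given the 12-week life-expectancy criterion in Protocol 5.2.1); response independent of survival, so the true ratio is 1.

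**Formula.** Let S be the survival function, C the cutoff and p the chance that a subject alive at day d responds then. Per subject enrolled:

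- responder deaths = p × [S(d) − S(C)]
- responder person-time = p × [d × S(d) + ∫ S(t) dt from d to C]
- non-responder deaths and person-time = totals for all subjects minus the above
- ratio = responder death rate / non-responder death rate

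**Worked case: constant hazard, median 6 months, 21% respond at Day 29, none later.**

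- λ = ln 2 / (6 × 30.4375) = 0.003796 per day; S(29) = 0.8958; S(C) = 0.0625.
- Responder deaths: 0.21 × (0.8958 − 0.0625) = 0.1750.
- Responder person-time: 0.21 × (29 × 0.8958 + 0.8333/0.003796) = 51.56 days.
- Non-responder deaths: 0.9375 − 0.1750 = 0.7625. Person-time: 247.0 − 51.56 = 195.4 days.
- Ratio: (0.1750/51.56) / (0.7625/195.4) = 0.87.
- Responder median: 29/30.4375 + 6 = 7.0 months. The non-responder median solves 0.79 × S(t) / (1 − 0.21 × 0.8958) = 0.5, so S(t) = 0.514 and t = 5.8 months.

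**Null ratios for true medians of 6 / 10 / 12 months.** The columns give the response probability at Days 29, 85 and 169 for subjects alive and not yet responding.

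| Hazard | .21, 0, 0 | .12, .06, .05 | .08, .10, .10 |
|---|---|---|---|
| Falling | .804 / .841 / .850 | .693 / .735 / .747 | .616 / .662 / .675 |
| Constant | .870 / .905 / .914 | .763 / .809 / .822 | .688 / .743 / .758 |
| Rising | .928 / .956 / .962 | .830 / .879 / .891 | .762 / .826 / .842 |

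Under constant hazard the medians run from 7.0 v 5.8 to 13.0 v 11.8 months when all responses come at Cycle 2. When responses are spread they run from 8.9 v 5.2 to 14.2 v 11.4 months.

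**Timing of the first marrow.** With constant hazard and responses at that marrow only, the ratio is 0.90–0.93 at Day 22, 0.84–0.89 at Day 36 and 0.93–0.95 for an unscheduled marrow at Day 15.

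**Second check.** A separate simulation used Cox hazard ratios, 400,000 subjects per setting, exponential survival with medians of 6, 9 or 12 months, and 30% to 80% of latent responses at the first assessment. It gave 0.68–0.87 at 21% observed response and 0.54–0.82 at an assumed 45%.

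**After the repair.** From a landmark at Day 29 or Day 85, among subjects alive and with response fixed there, the null ratio is 0.99–1.01.

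**A single trial of 82.** Across the three hazards, the responder median is the higher one in 56–76% of null trials (Cycle 2 only) or 67–97% (spread), against 48–53% after a landmark.

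**OS by best MRD, constant hazard.** 0.85–0.90 if samples within a subject are independent; 0.93–0.95 at within-subject correlation 0.5; 0.97–0.98 at 0.8; 0.99–1.00 at 1.

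**The case against.** The strongest reply is that little depends on this split. SAP 9.0 plans no formal testing, the OS analysis in Protocol 8.1.3.1.4 is unsplit, and SAP 8.1.7 states no comparison between groups. That stands, and it limits the rank of the point. It does not make the displayed medians interpretable.

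The size is also uncertain. Median OS, hazard shape and response timing are all assumed. The 21% is a CR rate, whereas the comparison group is non-CR/non-CRh, so the relevant responder share is CR + CRh, which the documents do not give. A larger share makes the bias larger, as the 45% setting shows. Noise in one trial is also wide: with constant hazard, Cycle 2 responses only and a 6-month median, 95% of null trials of 82 give a ratio between 0.49 and 1.55. With early responses and a rising hazard the bias is small (0.93–0.96). None of this changes its direction in expectation.

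On the remedy, initiation of Cycle 2 is a subject-specific date that can depend on response, because Protocol 6.1.8.3 links holding of venetoclax to remission with cytopenia. With initiation delayed by 7 to 28 days in half of responders, the simulated null ratio was still 0.99–1.015. That landmark does also drop living subjects who stop before Cycle 2, and a marrow taken after Day 1 within the window would be missed. Leaving several options open also invites choice after the fact, so the landmark should be named in advance.

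The MRD point is weaker: it is exploratory, and the effect may be close to zero.

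**Conclusion.** The concern holds. OS starts at first dose, the groups depend on a later event that requires survival, and neither document plans a landmark or time-dependent OS analysis.

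With response unrelated to survival, the planned split gives an expected ratio below 1 in all 27 settings, from 0.62 to 0.96. These sizes rest on the assumed survival and response patterns; the direction does not. OS for all subjects, response rates and durations that start at response are not affected. This is something the sponsor should change; no primary conclusion depends on it.

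**What to change.** In SAP 8.1.7, add OS from a landmark among subjects alive and under observation, with response status fixed there and time counted from there. The options are initiation of Cycle 2, using the 8.1.4 responders and only subjects who reach it, and/or Cycle 4 Day 1. Name the main landmark before the analysis. Response as a time-dependent covariate is an alternative.

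Use this analysis for any responder comparison, label the ever-response curves from first dose as non-comparative, and keep OS for all subjects. In 8.1.12, apply the same landmark to OS by best MRD, using MRD values up to that point.

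The cost is SAP wording and modest programming on existing data, with no new collection. There are two downsides:

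- **Early deaths leave the split tables.** Of 82 subjects, about 2 to 12 die by Day 29 and 8 to 26 by Day 85 across the assumed hazards.
- **Later responders count as non-responders.** In the spread settings, 36–65% of responders come after Cycle 2 Day 1 and 13–29% after Cycle 4 Day 1.

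The earlier landmark loses fewer subjects, and the later one misclassifies fewer.

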8.1.9 Time to the First Event

For each analysis set, the distribution of time to event for each parameter described in below sections will be estimated using Kaplan-Meier methodology. Median time to the first event for each parameter listed below with the corresponding 95% CI will be provided from Kaplan-Meier estimation. All data available in the extracted database will be used for the analyses described in Section [8.1.9](#).

8.1.9.1 Transfusion

The transfusion data was designed to be collected during the treatment period and until the 30 day follow-up visit. Thus, the data included in this section is from the first dose date of study drug to the last dose of study drug + 30 days. Transfusion data will be summarized as RBC transfusion and platelet transfusion separately.

Time to 1st RBC/Platelet Transfusion After Achieving CR

Time to 1st RBC/platelet transfusion after achieving CR will be defined as number of days from achieving CR to the first RBC/platelet transfusion. If a subject did not have any RBC/platelet transfusion events, the subject's data will be censored at 30 days after the last dose date of study drug or death of any cause, whichever occurs earlier. Subjects who achieve CR will be included in the analysis.

Time to 1st RBC/Platelet Transfusion After Achieving CRh

Time to 1st RBC/platelet transfusion after achieving CRh will be defined as number of days from achieving CRh to the first RBC/platelet transfusion. If a subject did not have any RBC/platelet transfusion events, the subject's data will be censored at 30 days after the last dose date of study drug or death of any cause, whichever occurs earlier. Subjects who achieve CRh will be included in the analysis.

Time to 1st RBC/Platelet Transfusion After Achieving CR/CRh

Time to 1st RBC/platelet transfusion after achieving CR/CRh will be defined as number of days from achieving CR/CRh to the first RBC/platelet transfusion. If a subject did not have any RBC/platelet transfusion, the subject's data will be censored at 30 days after the last dose date of study drug or death of any cause, whichever occurs earlier. Subjects who achieve CR/CRh will be included in the analysis.

Time to the 1st RBC/Platelet Transfusion Before Achieving CR

Time to the 1st RBC/platelet transfusion before achieving CR will be defined as number of days from the 1st date of study drug to the 1st RBC/platelet transfusion before achieving CR. If a subject did not have any RBC/platelet transfusion before achieving CR, the subject's data will be censored at the date that CR is first achieved. Only subjects who achieve CR will be included in the analysis.

Time to the 1st RBC/Platelet Transfusion Before Achieving CRh

Time to the 1st RBC/platelet transfusion before achieving CRh will be defined as number of days from the 1st date of study drug to the 1st RBC/platelet transfusion before achieving CRh. If a subject did not have any RBC/platelet transfusion before achieving CRh, the subject's data will be censored at the date that CRh is first achieved. Only subjects who achieve CRh will be included in the analysis.

Time to the 1st RBC/Platelet Transfusion Before Achieving CR/CRh

Time to the 1st RBC/platelet transfusion before achieving CR/CRh will be defined as number of days from the 1st date of study drug to the 1st RBC/platelet transfusion before achieving CR/CRh. If a subject did not have any RBC/platelet transfusion before achieving CR/CRh, the subject's data will be censored at the date that CR/CRh is first achieved. Only subjects who achieve CR/CRh will be included in the analysis.

Time to 1st RBC/Platelet Transfusion from 60 Days After the First Dose of Study Drug

Time to 1st RBC/platelet transfusion from 60 days after the first dose of study drug will be defined as number of days from 60 days after first dose date of study drug to the first RBC/platelet transfusion. If a subject did not have any RBC/platelet transfusion, the subject's data will be censored at 30 days after the last dose date of study drug or death of any cause, whichever occurs earlier. This analysis will be performed for subjects who achieve CR, achieve CR/CRh, and don't achieve CR or CRh separately.

Time to First RBC/Platelet Transfusion from 1st Date of Study Drug

Time to 1st RBC/platelet transfusion from 1st date of study drug will be defined as number of days from first dose date of study drug to the first RBC/platelet transfusion. If a subject did not have any RBC/platelet transfusion, the subject's data will be censored at 30 days after the last dose date of study drug or death of any cause, whichever occurs earlier. This analysis will be performed for subjects who achieve CR, achieve CR/CRh, and don't achieve CR or CRh separately.

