8.1.9.2 Time to the First Hospitalization due to SAE

Analyses of adverse events will include only "treatment-emergent" events. "Treatment emergent adverse events" are defined as any adverse events that first occur on or after the date of first dose of study drug and with an onset date no more than 30 days after the last dose date of study drug. Thus, the data included in this section is from first dosing of study drug to last dose date of study drug + 30 days.

Time to 1st Hospitalization After Achieving CR

Time to the 1st hospitalization after achieving CR will be defined as number of days from achieving CR to the first hospitalization. If a subject did not have any hospitalization, the subject's data will be censored at 30 days after the last dose date of study drug or death of any cause, whichever occurs earlier. Subjects who achieve CR will be included in the analysis.

Time to 1st Hospitalization After Achieving CRh

Time to the 1st hospitalization after achieving CRh will be defined as number of days from achieving CRh to the first hospitalization. If a subject did not have any hospitalization, the subject's data will be censored at 30 days after the last dose date of study drug or death of any cause, whichever occurs earlier. Subjects who achieve CRh will be included in the analysis.

Time to the 1st Hospitalization After Achieving CR/CRh

Time to the 1st hospitalization from achieving CR/CRh will be defined as number of days from achieving CR/CRh to the 1st hospitalization. If a subject did not have any hospitalization, the subject's data will be censored at 30 days after the last dose date of study drug or death of any cause, whichever occurs earlier. Subjects who achieve CR/CRh will be included in the analysis.

Time to the 1st Hospitalization Before Achieving CR

Time to the 1st hospitalization before achieving CR will be defined as number of days from the 1st date of study drug to the 1st hospitalization before achieving CR. If a subject did not have any hospitalization event, the subject's data will be censored at date that CR is first achieved. Subjects who achieve CR will be included in the analysis.

Time to the 1st Hospitalization Before Achieving CRh

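### In 20 of the 32 time-to-first-event definitions in SAP 8.1.9, death is censored in a Kaplan-Meier analysis, so the median is too short and 1-KM exceeds the cumulative incidence

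*SAP*

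**What the plan says.** The SAP document holds an efficacy plan and a safety plan. This point concerns sections 8.1.9 and 8.1.10 of the efficacy plan.

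- **Estimator.** For each analysis set, "the distribution of time to event for each parameter described in below sections will be estimated using Kaplan-Meier methodology".
- **Output.** "Median time to the first event for each parameter listed below with the corresponding 95% CI will be provided from Kaplan-Meier estimation". No event probability at a fixed time is listed.
- **Main censoring rule.** Each of the four event types has eight definitions. Five of them (after or from CR, CRh and CR/CRh; from day 60; from first dose) have event-free subjects censored at "30 days after the last dose date of study drug or death of any cause, whichever occurs earlier".
- **The other three.** The definitions covering the time before CR, CRh and CR/CRh stop at response. For transfusion before CR, "the subject's data will be censored at the date that CR is first achieved" and "Only subjects who achieve CR will be included in the analysis". Hospitalisation follows the same pattern: "the subject's data will be censored at date that CR is first achieved".
- **Window.** For transfusion, "the data included in this section is from the first dose date of study drug to the last dose of study drug + 30 days". The hospitalisation and haemorrhage sections set the same limit through the treatment-emergent definition.
- **Displays by response.** The day-60 and first-dose definitions are run separately for subjects with CR, with CR/CRh, and with neither.
- **8.1.10.** All four recurrent-transfusion definitions censor at the same earlier-of date, but that section names no estimator.
- **Sensitivity analyses.** 8.1.11 covers only duration of response and OS. No competing-risk estimator appears anywhere in the plan.

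**The concern.** Kaplan-Meier treats a censored subject as someone who could still have the event later, at the same rate as those still under observation. That is a reasonable model for a subject who is alive when observation stops. It is not one for a subject who has died, who can no longer be transfused, admitted, bleed or become infected. With death censored, the curve describes what would happen if death did not occur. Read as a statement about the treated patients, 1-KM is then too high, and the time by which half are said to have had the event is too early.

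The stake is interpretive. These outputs are shown side by side for responders and non-responders, and a reader will compare them. If more subjects die within the window in one group, the error is larger in that group and the comparison is shifted by something other than the event rate. Protocol 3.1 describes survival on low-dose cytarabine as short, so in-window deaths without a prior event are plausible, most of all among subjects who reach neither CR nor CRh.

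**Working it through.** The plan states no expected event rate, event count or precision for these analyses, so there is no figure to reproduce. The check has three steps.

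**1. Count the definitions by censoring rule (SAP 8.1.9.1 to 8.1.9.4).**

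| Definition | Per event type | Four event types | Event-free subjects censored at |
|---|---|---|---|
| After/from CR, CRh, CR/CRh | 3 | 12 | earlier of last dose + 30 days and death |
| From day 60; from first dose | 2 | 8 | earlier of last dose + 30 days and death |
| Before CR, CRh, CR/CRh | 3 | 12 | date of response |

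So 12 + 8 = 20 of 32 censor at death. The remaining 12 include responders only, and nobody in them can die before the censoring date. RBC and platelet versions are counted once. The serious-haemorrhage and serious-infection variants, planned by the same method if data allow, are not counted.

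**2. Size under assumed constant hazards.** Let a be the monthly event hazard and b the monthly hazard of death without a prior event inside the window. Then:

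- 1-KM(t) = 1 − exp(−a·t)
- cumulative incidence(t) = a/(a+b) × [1 − exp(−(a+b)·t)]
- KM median = ln 2 / a
- cumulative-incidence median = −ln[1 − 0.5(a+b)/a] / (a+b), if a/(a+b) > 0.5

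Take 1-KM = 60% at 12 months, so a = −ln(0.4)/12 = 0.0764. For a 30% 12-month death risk, b = −ln(0.7)/12 = 0.0297. The cumulative incidence is 0.0764/0.1061 × (1 − 0.4 × 0.7) = 0.720 × 0.72 = 51.8%, an excess of 8.2 points. The KM median is 0.693/0.0764 = 9.1 months, and the cumulative-incidence median is 11.2 months. Over the range:

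| 12-month death risk (assumed) | 1-KM | Cumulative incidence | Excess (points) | KM median (months) | Cumulative-incidence median (months) |
|---|---|---|---|---|---|
| 10% | 60% | 57.4% | 2.6 | 9.1 | 9.6 |
| 20% | 60% | 54.7% | 5.3 | 9.1 | 10.2 |
| 30% | 60% | 51.8% | 8.2 | 9.1 | 11.2 |
| 50% | 60% | 45.5% | 14.5 | 9.1 | 15.7 |

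With 1-KM = 20%, the excess is 0.5 to 5.4 points for death risks of 5% to 50%. With 1-KM = 80%, it is 1.5 to 17.1 points.

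The table also shows the effect on a comparison. Two groups with the same event hazard but death risks of 10% and 30% would both show 60% by 1-KM, while their cumulative incidences differ by 57.4 − 51.8 = 5.6 points.

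**3. Simulation check.** The setting was N = 82 (the 600 mg group in SAP Table 3), 2000 replicates, 1-KM = 60%, and an end of treatment independent of event and death (exponential, median 6 months, plus 1 month). Mean 1-KM against mean Aalen-Johansen estimate at 12 months was 0.600 against 0.574 (10% death risk), 0.600 against 0.519 (30%) and 0.602 against 0.456 (50%). This agrees with the formulas.

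**The case against.** The strongest reply is that Kaplan-Meier with death censored is a recognised cause-specific summary, that the outputs are descriptive with no formal testing (SAP 9.0), and that proportions are reported elsewhere without it. Safety SAP 7.6.1 gives the number and percentage of subjects with adverse events. Section 7.6.5 splits treatment-emergent, Grade 3 or above and serious events by best response. Efficacy SAP 8.1.8 gives transfusion independence as a proportion with an exact interval.

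Much of this stands. It limits the consequence, and it rules out a stronger reading that a reader might infer: that every analysis in 8.1.9 is affected and that the plan overstates how many patients ever have these events. The documents do not support that:

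- The 12 definitions ending at response contain no censored deaths.
- The planned output is a median, not a proportion.
- Observation ends at last dose + 30 days, so nothing is claimed about what patients ever experience.
- Grade 5 means death in Protocol 6.1.2 and falls within Grade 3 or above, so fatal haemorrhages and infections count as events. Only deaths without a prior qualifying event are censored.
- No document gives an in-window death rate, overall or by response. Higher in-window mortality among non-responders is plausible but not documented.

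Random error will also be large in the small displays. SAP Table 7 targets a CR rate of 21% of 82, about 17 subjects. Ignoring censoring, the standard error of a proportion near 54.7% is then √(0.547 × 0.453/17) = 0.12, or 12 points, which exceeds the bias in most of the scenarios above.

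What does not stand is that the percentages elsewhere repair these outputs. They are not timed from CR, CRh or day 60, and they do not correct the medians. For transfusion, safety SAP 7.6.4 summarises only the number of transfusions. Nor does the plan say that the medians are cause-specific.

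**Conclusion.** The point holds for the 20 definitions that censor at death. In these, the Kaplan-Meier median is too short and 1-KM is above the cumulative incidence whenever subjects die in the window without the event. The error differs between the CR, CR/CRh and non-CR/CRh displays if in-window mortality differs between them. The direction is certain. The size is not, because the documents give no in-window death rate. Over the assumed range the 12-month excess runs from about 0.5 to 17 points, and the effect on the median from negligible to several months. These figures rest on constant hazards and on end-of-treatment censoring unrelated to the event.

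The four definitions in 8.1.10 share the censoring rule and would have the same problem under Kaplan-Meier, although no estimator is named there. This is an inexpensive improvement to descriptive outputs. It does not bear on the ORR, CR, CR + CRh or OS results.

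**What to change.** For the 20 definitions in 8.1.9 and the four in 8.1.10, add to the SAP:

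- the Aalen-Johansen cumulative incidence of the first event (first recurrent transfusion in 8.1.10), with death before that event as a competing event, at fixed times such as 3, 6 and 12 months with 95% CIs;
- the number of subjects in each display with the event, dead without it, and censored alive at the end of the window;
- a label on every retained Kaplan-Meier median stating that it is cause-specific, with death censored;
- a named estimator in 8.1.10.

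Leave the 12 definitions that end at response as they are for this purpose.

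No new data are needed, because death dates already enter the censoring rule. The cost is SAP wording and one more set of descriptive outputs. The change deals with death only. It still treats subjects alive at last dose + 30 days as ordinarily censored, and a table footnote should say so.
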